Weighing Risks and Benefits of Laparoscopic Anti-Reflux Surgery in Patients With Idiopathic Pulmonary Fibrosis

NCT01982968

Document Date: 08 Apr 2016

WEIGHING RISKS AND BENEFITS OF LAPAROSCOPIC ANTI-REFLUX SURGERY IN PATIENTS WITH IDIOPATHIC PULMONARY FIBROSIS (WRAP-IPF): **A PHASE II CLINICAL TRIAL**

Version 6.0 (amendment #4.1) Version date: 11 Dec 2015

Protocol Summary

TREATMENT	Laparoscopic anti-reflux surgery				
CLINICALTRIALS.GOV IDENTIFIER	NCT01982698				
PROTOCOL TITLE	Weighing Risks and benefits of Laparoscopic Anti- Reflux Surgery in Patients with Idiopathic				
DIAGNOSIS AND MAIN CRITERIA	Pulmonary Fibrosis (WRAP-IPF)				
FOR INCLUSION	Confirmed idiopathic pulmonary fibrosis (IPF) and				
FOR INCLUSION	evidence of abnormal acid gastro-esophageal				
	reflux (GER) by 24-hour pH testing (DeMeester score of >14.7)				
STUDY OBJECTIVES	To demonstrate slowed decline of forced vital				
	capacity (FVC) through anti-reflux surgery				
	compared with standard care.				
STUDY DESIGN	Multi-center, randomized, un-blinded				
TREATMENT REGIMEN	Laparoscopic anti-reflux surgery or standard care.				
DURATION OF STUDY	52 weeks				
PARTICIPATION					
NUMBER OF SUBJECTS	Approximately 58 (randomized in a 1:1 ratio)				
NUMBER OF SITES	6 sites (U.S. only)				
PRIMARY ENDPOINTS	Change in FVC from baseline to 48 weeks				
SECONDARY ENDPOINTS	Mortality				
	Non-elective hospitalization				
	Acute exacerbation				
	Disease Progression				
	Change in UCSD SOBQ score				
	Change in SGRQ score				
	Time to death, acute exacerbation, or non-elective				
	hospitalization (composite endpoint)				
	Time to death, acute exacerbation, non-elective				
	hospitalization, or disease progression (composite				
	endpoint)				
	Categorical change in FVC				
	Change on cough visual analog scale (VAS)				

Change in ICECAP-O score
Change in EuroQOL EQ-5D score
Change in 6-minute walk distance (6MWD)
Reduction in acid GER assessed by serial pH
testing and GER questionnaire
Quantitative change in HRCT fibrosis score

 Study Sponsor:
 National Heart Lung and Blood Institute, NIH

 Study Chairs:
 [name] – UCSF [name] – University of Washington

 Steering Committee Members
 [name] - Duke University

12.2. CONFIDENTIALITY AND HEALTH INSURANCE PORTABILITY AND ACCOUNTABILITY ACT (HIPAA)	
CONSIDERATIONS	31
13. INVESTIGATOR AGREEMENT	33
14. REFERENCES	34

List of Tables

Table 1. Table of Study Visits.

Table 2. Final Diagnosis in the Evaluation of Suspected Acute Exacerbations.

Table 3. Enrollment requirements for varying effect size and power.

List of Figures

Figure 1. Laparoscopic surgery was associated with increased survival compared to no therapy.

Figure 2. Change in FVC before (pre) and after (post) laparoscopic anti-reflux surgery.

List of Abbreviations

6MWD	6-minute walk distance
6MWT	6-minute walk test
ABG	arterial blood gas
AE	adverse event
AEx	acute exacerbation
BAL	bronchoalveolar lavage
CRF	case report form
DCC	Data Coordinating Center
DLCO	diffusing capacity of the lung for carbon monoxide
DSMB	Data and Safety Monitoring Board
eCRF	Electronic case report form
FVC	forced vital capacity
GER	Gastroesophageal reflux
HIPAA	Health Insurance Portability and Accountability Act
HRCT	high-resolution computed tomography
ICECAP-O	ICEpop CAPability measure for Older People
ILD	interstitial lung disease
IPF	idiopathic pulmonary fibrosis
IRB	institutional review board
MOP	Manual of Operating Procedures
NHLBI	National Heart Lung and Blood Institute
NIH	National Institutes of Health (U.S.)
PFT	pulmonary function test
PI	principal investigator
QOL	quality of life
SAE	serious adverse event
SAP	statistical analysis plan
SGRQ	St. George's Respiratory Questionnaire
UCSD SOBQ	University of California at San Diego Shortness of Breath Questionnaire
VAS	Visual Analog Scale

WEIGHING RISKS AND BENEFITS OF LAPAROSCOPIC ANTI-REFLUX SURGERY IN PATIENTS WITH IDIOPATHIC PULMONARY FIBROSIS (WRAP-IPF): A PHASE II CLINICAL TRIAL

1. Summary

This protocol proposes to test the following hypothesis: Treatment with laparoscopic antireflux surgery in subjects with idiopathic pulmonary fibrosis (IPF) and abnormal gastroesophageal (GER) reflux will slow the decline of forced vital capacity (FVC) over 48 weeks.

This study will randomize approximately 58 subjects with IPF and abnormal acid reflux on 24-hour pH monitoring to laparoscopic anti-reflux surgery or standard care (randomization ratio 1:1). Subjects will be followed for 52 weeks or until the time of lung transplantation or death.

2. Hypothesis and Specific Aims

2.1. Study Hypothesis

Our primary hypothesis is that the reduction of abnormal GER with laparoscopic anti-reflux surgery will slow the progression of IPF as measured by FVC. We further hypothesize that laparoscopic anti-reflux surgery will reduce the frequency of acid reflux, will be safe and well tolerated, will improve symptoms and quality of life, and will reduce the incidence of acute exacerbation, hospitalization, disease progression and death. Specifically, we will address the following aims:

2.2. Specific Aim 1

We aim to determine the impact of laparoscopic anti-reflux surgery on change in FVC over 48 weeks in patients with IPF and abnormal GER.

2.3. Specific Aim 2

We aim to correlate the reduction in acid reflux events with the change in FVC over 48 weeks in patients with IPF and abnormal GER.

2.4. Specific Aim 3

We aim to determine the safety of laparoscopic anti-reflux surgery in patients with IPF and abnormal GER.

2.5. Specific Aim 4

We aim to explore the impact of laparoscopic anti-reflux surgery on key secondary endpoints over 48 weeks in patients with IPF and abnormal GER.

2.6. Specific Aim 5

To identify molecular markers of IPF disease activity and gastroesophageal reflux in biological samples from patients with IPF and abnormal GER.

3. Background and Significance

Idiopathic pulmonary fibrosis (IPF) is a chronic progressive lung disease of unknown cause and increasing prevalence in the United States.^{1,2} An estimated 100,000 Americans will die from IPF this year, and aside from lung transplantation, which only 1% will receive, there is no FDA-approved therapy.

Over the last decade, a potential role for gastroesophageal reflux (GER) in the progression of IPF has been suggested.³ This is based on several observations: First, it is clear that the overwhelming majority of patients with IPF have abnormal GER.⁴⁻⁶ Second, small case series of patients with IPF treated for GER demonstrated stabilization of pulmonary physiology and oxygenation.^{7,8} Third, the treatment of GER has been associated with improved survival in two large, independent retrospective cohorts of patients with IPF.⁹

Importantly, there are no prospective, randomized data addressing the treatment of GER in IPF and there is a real chance that the data collected to date are misleading. A prospective, controlled trial is essential to answer this question.

The mechanistic hypothesis for GER causing progression of IPF is as follows. Abnormal GER is a known risk factor for microaspiration of gastric contents.^{10,11} In patients with IPF, microaspiration may be an important contributor to disease progression through increasing the alveolar epithelial stress and abnormal repair characteristic of the disease.^{12,13} In support of this are data from patients with IPF experiencing acute exacerbation of their disease that demonstrate increased levels of pepsin in the bronchoalveolar lavagate compared to stable IPF patients.¹⁴

Both acid and non-acid GER may be important to disease progression in IPF based on data from animal models that show aspiration of both acid and non-acid refluxate causes pulmonary fibrosis,¹⁵⁻¹⁷ and data from IPF patients suggest an increased benefit of

laparoscopic anti-reflux surgery over medical antacid therapy alone.⁹ Surgical treatment for GER with laparoscopic anti-reflux surgery reduces the incidence of all GER, both acid and non-acid; medical treatment for GER does not reduce the incidence of GER substantially – instead it simply reduces the acidity of the refluxate. Laparoscopic anti-reflux surgery has been safely performed in patients with IPF and other forms of advanced lung disease awaiting lung transplantation.^{8,18,19}

Together, these data provide an argument for a possible benefit to the treatment of abnormal GER in patients with IPF and associated GER, a fact recently recognized by the ATS/ERS/JRS/ALAT evidence-based guidelines committee authors and others.^{1,20} The data further suggest that therapy with laparoscopic anti-reflux surgery, that reduces the incidence of both acid and non-acid reflux, is the most appropriate intervention to test.

4. Preliminary Studies

4.1. Animal models

[figure not shown]
Animal models show that both the acid and non-acid components of gastroesophageal refluxate are relevant. In one animal model of acute gastric acid aspiration, widespread collagen deposition developed in the lungs within two weeks.¹⁵ In other animal models investigating chronic aspiration of various components of the gastric refluxate showed that development of lung fibrosis was independent of the acidity of the aspirate, and suggesting perhaps gastric contents (e.g. bile, pepsin, or food particulates) were responsible.^{16,17} These data support the concept that there are multiple components of the gastroesophageal refluxate (both acid and non-acid) that could contribute to ongoing alveolar epithelial stress in patients with IPF through chronic aspiration into the lungs.

4.2. Retrospective data in patients with IPF

Abnormal GER is highly prevalent in patients with IPF, with a reported 67-88% of patients demonstrating abnormal 24-hour pH monitoring.⁴⁻⁶ The most recent and largest study studied 65 consecutive patients with IPF regardless of symptoms or a pre-existing diagnosis of abnormal GER.⁵ All patients underwent 24 hour pH monitoring and esophageal manometry testing. The prevalence of abnormal GER was 87%, with 63% demonstrating abnormal reflux into the proximal esophagus. Only 47% of patients had classic GER symptoms of heartburn and dyspepsia. Manometry was largely within normal limits. These and other data have led investigators to hypothesize that abnormal GER might contribute to the progression of IPF through predisposing patients to aspiration of gastroesophageal

[figure not shown]
refluxate that in turn causes chronic stress to the alveolar epithelium.³ A small case series of four patients demonstrated relative stabilization of forced vital capacity (FVC) and diffusion capacity for carbon monoxide (DLCO) with medical therapy for GER.⁷ A second case series of fourteen patients with advanced IPF on the waiting list for lung transplantation demonstrated stabilization of oxygen requirements after laparoscopic anti-reflux surgery compared to 31 patients with IPF on the waiting list for lung transplantation that did not undergo laparoscopic anti-reflux surgery.⁸

[figure not shown]
Retrospective data from a cohort of IPF patients followed as part of a clinical trials consortium demonstrated a reduction in the rate of decline in FVC over 30 weeks for subjects taking anti-acid therapy.²¹ Additional retrospective data from the University of California San Francisco and the Mayo Clinic, Rochester demonstrated that a history of laparoscopic anti-reflux surgery was associated with prolonged survival time in patients with IPF (Figure 1).⁹ Medical therapy (mostly with proton pump inhibitor (PPI)) appeared less effective. These data are limited by their retrospective nature, but support the hypothesis that treatment of abnormal GER in IPF slows progression of disease, and that laparoscopic anti-reflux surgery is more effective that medical therapy.

A total of 14 patients with progressive IPF (mean age 63 years, mean FVC 66 percent predicted (range 40-99%)) and abnormal GER who underwent laparoscopic anti-reflux surgery at University of Washington had pre- and post-surgical FVC measurements obtained (Figure 2). FVC was assessed prior to the surgery (mean of 105 days prior to anti-reflux surgery) and post-surgery (mean of 115 days following the anti-reflux surgery). Over

the average of 7 months between the pre- and post-anti-reflux surgery assessments, the mean FVC increased by 0.08L (3.5 percent predicted) and the majority of participants (10/14) experienced an increase in FVC. All patients were discharged after the standard one night of post-operative observation without any medical or surgical complications.

5. Methods

5.1. Inclusion Criteria

Only subjects with confirmed IPF, abnormal GER on 24-hour pH monitoring (as defined by a DeMeester score of > 14.7) and esophageal manometry that is acceptable for full laparoscopic anti-reflux surgery will be eligible for this study. Subjects must be able to provide informed consent and be willing to undergo laparoscopic anti-reflux surgery.

5.2. Diagnosis of Idiopathic Pulmonary Fibrosis

Subjects will be evaluated for IPF at the enrolling center. Study investigators will follow the most current ATS/ERS/JRS/ALAT evidence-based guidelines in making this determination.

A subject with suspected interstitial lung disease (ILD) should be evaluated for secondary causes including, but not limited to, environmental exposures, drugs, and systemic diseases. Presence of any of these findings felt to be significant enough to cause an ILD should disqualify the subject from entry into the trial.

5.3. Exclusion Criteria

- 1. FVC < 50% predicted
- 2. FEV1/FVC ratio < 0.65
- 3. Resting room air PaO2 < 60mm Hg
- 4. Unable to walk 50 meters on 6 minute walk test
- 5. Recent acute respiratory illness in last 12 weeks
- 6. Participated in an interventional clinical trial for an IPF therapy in the last 28 days (subjects may be screened, but cannot be enrolled until 28 days after trial participation) [Note: open-label extensions or expanded access programs (EAPs) for pirfenidone or nintedanib are not considered interventional clinical trials and are not exclusionary.]
- 7. Listed for lung transplantation at screening
- 8. Unable to safely undergo full (complete) laparoscopic gastric anti-reflux surgery (i.e. not a partial fundoplication), in the judgment of the investigators
- 9. History of esophageal / bariatric / gastric surgery
- 10. History of cancer (other than non-melanoma skin cancer) in the last 3 years
- 11. Pregnant at the time of screening or enrollment
- 12. Unlikely to obtain pre-authorized approval from a third party payer for laparoscopic anti-reflux surgery and related costs in the opinion of the investigators.
- 13. Life expectancy < 48 weeks due to another illness
- 14. BMI > 35
- 15. Known severe pulmonary hypertension (mean pressure > 35 mm Hg on RHC; RVSP > 50 mm Hg on ECHO)

5.4 Study Design and Study Visits

Subjects who appear to meet entry criteria will review the informed consent (a written description of the purpose, procedures, and risks of the study) with the principal investigator (PI), co-investigator, or study coordinator, and all questions will be answered. The informed consent form will be signed by the subject at the beginning of the screening visit. No protocol-specific procedures will be performed until the subject has signed and dated an informed consent form. This includes the screening procedures.

The enrollment visit should occur within 90 days of the screening visit. However, it is preferred that the enrollment visit occur within 28 days of the screening visit to avoid repeating procedures.

All follow-up study visits will occur within 10 business days of their designation (e.g. week 12 will occur +/- 10 business days from the week 12 timepoint).

		Visit							
Study Procedure	Procedure details	Screen V1	Enroll V2	Surgery V2A	Wk 12 V3	Wk 24 V4	Wk 36 V5	Wk 48 V6	Wk 52
Medical history	 Complete medical history 	•							
Physical examination	Physical exam	•			•	•	•	•	
Documentation of GER	 Symptom questionnaire 	٠				•		•	Р
Assessment of esophageal motility and pH	> pH and manometry	•+				•&			H O N
Laparoscopic anti- reflux surgery *				•					Е
Bronchoscopy *				•				•^	V
Spirometry (Hand-held)									I S
Spirometry (Office based)		٠	•#		•!	•!	•!	•!	I T
DLCO			•		•!	•!		•!	
Arterial blood gas		•			•	•		•	
6 minute walk test		•	●#		•	•		•	
HRCT			•@					•	
Patient reported outcomes	 UCSD SOBQ Cough VAS SGRQ ICECAP EQ-5D 		•		•	•	•	•	
Blood collection			•		•	•	•	•	

Table 1. Table of Study Visits

* These procedures will be performed only in those subjects randomized to surgery.

+Does not need to be completed if done within 6 months of V2 at the study site in accordance with the study protocol.

@ Does not need to be completed if done within 3 months of V2 at the study site in accordance with the study protocol.

Only performed if V2 performed > 28 days after V1.

^ This is an optional procedure and will only be performed if the subject has consented for it.

! If a subject has undergone fundoplication surgery (regardless of treatment assignment) within 8 weeks of this visit date, the subject should not undergo this procedure.

& The pH and manometry should be done a minimum of 12 weeks after surgery, and only in those subjects randomized to surgery.

At screening, all potential subjects will undergo a complete medical history, physical examination and testing (spirometry (performed pre-bronchodilator), arterial blood gas, GER symptom questionnaire, and 6 minute walk testing) with assessment of eligibility according to the inclusion and exclusion criteria. All potential subjects who meet entry criteria based on these assessments will undergo 24-hour pH testing and esophageal manometry, unless these procedures have been performed within 6 months of the enrollment visit (Visit 2) at the study site in accordance with the study protocol.

Subjects meeting eligibility criteria will return for an enrollment visit within 90 days (but preferably within 28 days), and will complete baseline evaluations as outlined in this protocol, including:

- Physical examination
- Diffusing capacity of the lung for carbon monoxide (DLCO)
- High-resolution computed tomography (HRCT) (unless performed in the past 3 months according to study protocol and available for review and databasing)
- Patient reported outcome questionnaires
 - UCSD Shortness of Breath Questionnaire (UCSD SOBQ)
 - St. George's Respiratory Questionnaire (SGRQ)
 - Cough visual analog scale (VAS)
 - ICECAP-O
 - EuroQOL EQ-5D
- Blood collection (5 tsp) for measurement of biomarkers

If the enrollment visit occurs within 28 days of screening, the screening values for spirometry and the 6 minute walk test (6MWT) will be recorded as the baseline values. If the subject is unable to return for enrollment until more than 28 days from screening, the spirometry and 6MWT procedures will need to be repeated, and those measurements recorded as the baseline values.

Enrolled subjects will be randomized to either receive anti-reflux surgery or standard medical care.

Subjects randomized to anti-reflux surgery will undergo additional evaluations as directed by the surgical team (these may include but are not limited to esophagram, endoscopy, and echocardiography) and will have pre-surgical evaluation by anesthesiology. These subjects

will undergo preapproval for billing the laparoscopic anti-reflux surgery and related activities and tests to the subject's insurance (all other study procedures will be paid for by the study). In the unlikely event that a randomized subject is denied authorization, the subject will not have surgery but will be followed on an intention to treat basis. All subjects in the surgical arm will receive a bronchoscopy at the time of surgery. Bronchoscopy is a separate procedure from the surgical intervention. Bronchoscopy will be performed according to standardized protocol and samples (BAL and endobronchial brushings) will be collected. These patients will then undergo surgery according to study protocol (see section 8). They will have a post-operative visit with the surgeon at approximately 2 weeks to ensure appropriate recovery.

Subjects randomized to no surgery will be followed clinically. If there is evidence of significant disease progression (defined by a relative decline in FVC of \geq 10% over 24 weeks or longer), these patients will be allowed to undergo laparoscopic anti-reflux surgery as part of the clinical trial. These patients will otherwise complete the study visits as scheduled.

All subjects in the study will be provided with a home spirometer and instructed to perform spirometry daily throughout the course of the clinical trial. Subjects who are randomized to surgery will be instructed to halt daily spirometry from the date of their surgery until they return to the site for the week 12 visit.

Subjects will be blinded to the results of the home spirometry measurements. Subjects will be instructed to bring home spirometers to each study visit so that data can be downloaded and sent to the DCC for databasing. Subjects will have the option after study completion to keep the home spirometer for personal use.

Safety assessments: Subjects will be contacted by telephone for safety assessments in months where no study visit occurs (months 1, 2, 4, 5, 7, 8, 10, 11) and at week 52. The calls should visits will occur within 10 business days of their designation (e.g. month 1 will occur +/- 10 business days from the month 1 timepoint). One month is defined as 28 days. These phone calls will involve confirming the subject's vital status and asking questions about serious adverse events or adverse events related to the surgical procedure, for subjects randomized to surgery.

At weeks 12, 24, and 36, and 48, subjects will return for evaluation. Each visit will include:

- Physical examination
- Spirometry
- DLCO (except week 36)
- Arterial blood gas (ABG) measurement (except week 36)
- 6MWT (except week 36)
- Patient reported outcome questionnaires (USCD SOBQ, SGRQ, Cough VAS, ICECAP-O, EuroQOL EQ-5D)
- GER questionnaire (at weeks 24, and 48 only)
- Manometry and 24-hour pH testing (at week 24 only, and for subjects randomized to surgery only)
- Blood collection (5 tsp) for measurement of biomarkers
- HRCT (at week 48 only)
- Bronchoscopy with collection of samples (at week 48 only, and for subjects randomized to surgery who have consented to the procedure). This procedure will be performed in an outpatient setting.

At week 52, or 4 weeks after the final study visit, subjects will be contacted by the site coordinator for updates on outstanding AEs and serious adverse events (SAEs).

Study staff may make a long-term follow up at one or more times after subjects complete the study visits to request additional information or talk to subjects about clinical or research issues that are relevant to patients with IPF.

If a subject withdraws early from the study, s/he will be asked to return to complete the battery of assessments scheduled at week 48.

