6.2. Secondary Endpoints

The secondary endpoints of this study will be:

- Disease progression
- Categorical change in FVC
- Acute exacerbation
- Non-elective hospitalization
- Mortality
- Time to disease progression
- Time to categorical change in FVC, acute exacerbation, or death (composite endpoint)

- Time to non-elective hospitalization or death (composite endpoint)
- Change in UCSD SOBQ score (continuous and categorical)
- Change in SGRQ score (continuous and categorical)
- Change on cough visual analog scale (VAS)
- Change in ICECAP-O score (continuous and categorical)
- Change in EuroQOL EQ-5D scores (continuous and categorical)
- Change in 6-minute walk distance (6MWD) (continuous and categorical)
- Reduction in acid GER by serial pH testing and GER questionnaire
- Quantitative change in HRCT fibrosis score and honeycombing

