6.3. Definition of Disease Progression

Disease progression is defined as one or more of the following: relative decline in FVC of \geq 10%; increase in UCSD SOBQ of \geq 5 points; suspected or definite acute exacerbation; death. Subjects and their treating physician will be notified of disease progression documented during the course of the study.

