The DCC will submit a detailed report of pre-specified AEs of interest and all SAEs monthly to NHLBI and DSMB chair. In addition, each SAE will be reported to NHLBI and DSMB chair by DCC within one business day after receiving the report. The DSMB Chair will review the information presented and determine if any additional information is needed, and/or a DSMB teleconference should be held. Guidelines for the DSMB procedures will be detailed in the DSMB charter.

8. Surgical Intervention

Subjects randomized to laparoscopic anti-reflux surgery will undergo preoperative evaluation by the surgical team after randomization. This will include a standard preoperative surgical assessment, anesthesia clearance, and other testing as medically indicated. During surgery, standard American Society of Anesthesiologists protocols will be used to monitor patients under general anesthesia. All subjects will be mechanically ventilated using the minimal tidal volumes and supplemental oxygen required to maintain adequate gas exchange. All subjects who undergo laparoscopic anti-reflux surgery will have a post-operative visit to insure appropriate recovery. There will be no scheduled study procedures during this visit.

Laparoscopic anti-reflux surgery generally involves the following steps. Individual patient issues may require modifications depending on the surgeon's intraoperative assessment. All efforts will be made to adhere exactly to the same surgical procedure, but if needed, the surgical team can deviate from the standardized protocol to ensure the safety of the patient and to achieve maximum beneficial results. Completion or modification of each stage will be documented in the clinical research form.

Step 1: Division of gastrohepatic ligament; identification of right crus of the diaphragm and posterior vagus nerve.

Step 2: Division of peritoneum and phreno-esophageal membrane above esophagus; identification of the left crus of diaphragm and anterior vagus nerve.

Step 3: Division of short gastric vessels.

Step 4: Creation of a window between gastric fundus, esophagus, and diaphragmatic crura.

Step 5: Placement of Penrose drain around the esophagus.

Step 6: Closure of crura.

Step 7: Insertion of the bougie into esophagus and through esophageal junction.

Step 8: Wrapping of gastric fundus around lower esophagus.

Step 9: Final inspection, removal of instruments and trocars from the abdomen, and closure of the port sites.

9. Data Management

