10.3. Analysis of Secondary Endpoints

The MMRM models will be applied to analyze the longitudinal data secondary endpoints. Regression modeling approaches using either the logistic regression model or Cox proportional hazards regression model will be employed for binary and time-to-event endpoints, respectively. All statistical analysis will be conducted using SAS version 9 or higher software. Statistical significance will be defined at the two-sided 0.05 level.

11. Study Administration

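### Surgery-arm subjects operated within 8 weeks before the week 12 visit miss that FVC reading while controls keep it, so the FVC part of two secondary time-to-event endpoints leans toward surgery by an amount the documents do not fix

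*Combined protocol and SAP*

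**What the plan says.** Table 1 (Section 5.4) schedules office spirometry at weeks 12, 24, 36 and 48. Its footnote to those visits says that if someone has "undergone fundoplication surgery (regardless of treatment assignment) within 8 weeks of this visit date, the subject should not undergo this procedure". The visit window is wide: "week 12 will occur +/- 10 business days from the week 12 timepoint".

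Surgery follows randomization and has no stated deadline. Section 5.4 says that subjects assigned to surgery "will undergo preapproval for billing the laparoscopic anti-reflux surgery and related activities and tests to the subject's insurance", and Section 8 that they "will undergo preoperative evaluation by the surgical team after randomization". A control may have surgery in the trial only on a relative FVC decline "of \geq 10% over 24 weeks or longer), these patients will be allowed to undergo laparoscopic anti-reflux surgery". Home spirometry also stops in the surgery arm from the operation until the week 12 visit (Section 5.4).

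Section 6.2 lists time to disease progression and "Time to categorical change in FVC, acute exacerbation, or death (composite endpoint"), together with disease progression and categorical FVC change as endpoints in their own right. Section 6.3 begins "Disease progression is defined as one or more of the following: relative decline in FVC of" at least 10%, and adds a rise of at least 5 points on the UCSD SOBQ, suspected or definite acute exacerbation, and death. For analysis, Section 10.3 says that either logistic regression or the "Cox proportional hazards regression model will be employed for binary and time-to-event endpoints, respectively". It has no rule for a skipped reading or for interval censoring.

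**The concern.** An FVC event can be recorded only when spirometry is done. If one arm has a reading that the other lacks, the same true FVC course gives different event dates. A fall present at week 12 is dated week 12 in a control, but week 24 at the earliest in a surgery subject whose week 12 test was barred. A fall that has reversed by week 24 is counted only in the control. A Cox model takes the recorded dates as the event times, so both effects make the FVC component look better under surgery without any benefit. Logistic models of the ever/never versions share the missing look.

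The trial is unblinded and small, and Section 10.3 tests secondary endpoints at two-sided 0.05. A tilt produced by the visit schedule would be hard to separate from benefit afterwards.

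**Working it through.** **Who misses which reading.** 12 - 8 = 4, so the cut-off for losing week 12 is surgery after about week 4. Ten business days is two weeks, so the cut-off lies between weeks 2 and 6. Surgery between the cut-off and the week 12 visit removes week 12. Surgery after about week 16 (24 - 8) moves the gap to week 24. A control needs a decline over at least 24 weeks, so counted from trial baseline none can cross over before week 12. A control who crosses over later has normally already met the 10% decline, so a reading barred after that costs no event.

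**Figures in the plan.** It gives none for these endpoints. Two others are used:
- Sample size: the two-sample t-test at 0.8 SD, two-sided 0.05 and 80% power needs 26 per arm. 52/0.90 = 57.8, so 58 as in Table 3, or 29 per arm.
- SD of one-year FVC change: about 0.25 L (Section 10.1).

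**Assumptions, because the documents are silent.** Baseline 2.6 L; mean loss 0.20 L per 48 weeks in both arms (no effect); a 10% relative decline for categorical FVC change, borrowed from Section 6.3 because Section 6.2 states no threshold; 12% exacerbation or death over 48 weeks. Visit SD v and slope SD s are paired so that √(s² + 2v²) is about 0.25 L.

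**Chance that a control shows an FVC event at week 12.** The mean change by then is -0.20/4 = -0.05 L and the threshold is about -0.26 L. The SD of the change is √((s/4)² + 2v²), and z = (-0.26 + 0.05)/SD.

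| v (L) | s (L) | SD of 48-week change | SD of week 12 change | z | Probability |
|---|---|---|---|---|---|
| 0.05 | 0.24 | 0.250 | 0.093 | -2.26 | 1.2% |
| 0.10 | 0.20 | 0.245 | 0.150 | -1.40 | 8.1% |
| 0.14 | 0.15 | 0.248 | 0.202 | -1.04 | 14.9% |

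The matching probability is zero for a surgery subject whose test is barred. Noise drives the result: with quiet readings few events fall at week 12, and those mostly persist to week 24.

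**Null hazard ratio, surgery vs control, for FVC change, exacerbation or death** (large-sample simulation; true value 1.00).

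| v (L) | All surgery subjects miss week 12 | Half miss it |
|---|---|---|
| 0.05 | 0.99-1.00 | 0.99-1.00 |
| 0.10 | about 0.95 | about 0.97 |
| 0.14 | about 0.89 | about 0.94 |

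A second set of inputs (baseline 2.75 L, loss 0.20 L, all missing week 12) gives 0.98 at v = 0.08 L, 0.92 at 0.12 L and 0.88 at 0.15 L. Its most extreme case (baseline 2.0 L, loss 0.30 L, v = 0.15 L) gives 0.82. No scenario leaned toward control.

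**Time to disease progression**, with SOBQ still read at week 12 (assumed mean rise 5-8 points, SD 12-15) and all missing week 12 FVC: 0.98 at v = 0.08 L and 0.92-0.93 at 0.15 L.

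**At 29 per arm** (log-rank, no effect, nominal 2.5% per tail, Monte Carlo error about 0.3 points). At v = 0.10 L there are about 31 events. The mean Z shift is -0.17 if all miss week 12 and -0.09 if half do. Rejections favouring surgery are 3.8% and 3.0%, against 3.0% with no skipping; total two-sided error is 5.7%, 5.0% and 5.6%. At v = 0.14 L with all missing, the tails are 5.7% for surgery and 0.8% for control.

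**Ever/never version**, FVC event alone, v = 0.10 L, all missing: 48.3% control vs 47.4% surgery. That gap is 0.009 × 29 = 0.26 of one patient per arm.

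**Common scoring from week 24 in both arms** returns the null hazard ratio to 1.00 within simulation error. With the second inputs it is 1.00 at v = 0.08 L and 0.99 at 0.15 L, with near-equal tails (2.3%/2.3% and 2.7%/2.9%). The interval-censored alternative was not simulated.

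**The case against.** The best reply is that the effect is negligible in a trial of this size. On mid-range inputs, even universal skipping moves the surgery-favouring tail by less than one percentage point. A material distortion needs both noisy spirometry and widespread skipping, and the documents establish neither. Resuming home spirometry at week 12, and requiring at least 12 weeks between surgery and the week 24 pH test, suggest that surgery was expected before week 12. They do not show whether it falls before week 4. These are also secondary endpoints, under an aim (Section 2.5) framed as exploratory. All of this stands and limits the size of the point.

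The balancing features do not remove it. Applying the footnote in both arms does not restore the week 12 comparison, since controls cannot have had per-protocol surgery by then. Home spirometry is halted over the same interval, and intention-to-treat follow-up does not supply a barred reading.

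A reader might infer more than the documents support:
- **That the whole surgery arm lacks week 12 FVC, or that the bias has a known size.** The share operated between about week 4 and week 12 is not given, and at v = 0.05 L the tilt all but vanishes.
- **That disease progression is distorted to the same degree.** SOBQ is not covered by the footnote and is collected at week 12 in both arms; exacerbations and deaths are captured too. Early post-operative dyspnea on SOBQ could push that endpoint the other way.
- **That the primary result is biased.** The primary analysis (Section 10.2) contrasts FVC at week 48, and this argument does not reach it.

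**Conclusion.** The point holds as a modest, one-directional flaw in the FVC component of time to categorical FVC change, acute exacerbation or death, in part in time to disease progression, and in the matching ever/never endpoints. The mechanism and its direction follow from the text; the size does not. It rests on the assumed 10% threshold, visit noise, baseline, rate of loss and share skipping. Within those assumptions the null hazard ratio for the composite runs from essentially 1.00 to about 0.89, with 0.82 only in a deliberately extreme case. At 29 per arm the shift in test error is small unless FVC noise is high and skipping is common. It is worth correcting because the remedy is cheap, not because it threatens the trial's main conclusion.

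**What to change.** In Section 10.3, state that the FVC component of these time-to-event and ever/never endpoints is scored from the week 24, 36 and 48 visits in both arms. Keep week 12 FVC in the MMRM. Report the Cox analysis of all visits as a sensitivity analysis.

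Scoring from week 24 does not give common reading times for a subject operated after about week 16, whose week 24 reading is barred. Add an interval-censored sensitivity analysis using each subject's actual spirometry dates to cover that case. Report the number of FVC visits missed under the footnote, by arm and visit, so that readers can judge how much was at stake.

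The cost is analysis-plan wording and minor programming. The downside is that some week 12 control events are dated later, or dropped if the fall has reversed by week 24; on the mid-range inputs about 8% of controls have such an event. The footnote and the clinical schedule stay as they are.
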